15.4 Data Integrity: See section *18.1*

16.0 Confidentiality

16.1 Data security: Information about study subjects will be kept confidential and managed according to the requirements of the Health Insurance Portability and Accountability Act of 1996 (HIPAA). Those regulations require a signed subject authorization informing the subject of the following:

- What protected health information (PHI) will be collected from subjects in this study
- Who will have access to that information and why
- Who will use or disclose that information
- The rights of a research subject to revoke their authorization for use of their PHI.

In the event that a subject revokes authorization to collect or use PHI, the investigator, by regulation, retains the ability to use all information collected prior to the revocation of subject authorization. For subjects that have revoked authorization to collect or use PHI, attempts should be made to obtain permission to collect at least vital status (i.e. that the subject is alive) at the end of their scheduled study period.

As disclosure of PHI is an aspect of participation in this study, there is a potential risk of unauthorized disclosure of PHI. To prevent this risk, we collect and store all PHI in a locked filing cabinet located in our keypad-controlled laboratory. Electronic PHI will be stored on HIPAA-compliant RedCap repositories. Pictures and other collected PHI will be stored on the University of Minnesota Box account, which is approved for the storage of PHI. No copies of the consent will be associated with the participant's medical or employment record.

17.0 Provisions to Monitor the Data to Ensure the Safety of Participants

17.1 Data Integrity Monitoring.

There will not be a designated data integrity monitor associated with this study. Instead, the PI will work with the study coordinator to ensure all data is collected, recorded, and maintained properly, and that regulatory and compliance procedures are followed accordingly.

The study case report form (CRF) is the primary data collection instrument for the study. All data requested on the CRF must be recorded. All missing data must be explained. If a space on the CRF is left blank because the procedure was not done or the question was not asked, write "N/D". If the item is not applicable to the individual case, write "N/A". All entries should be printed legibly in black ink. If any entry error has been made, to correct such an error, draw a single straight line through the incorrect entry and enter the correct data above it. All such changes must be initialed and dated. **DO NOT ERASE OR WHITE OUT ERRORS.** For clarification of illegible or uncertain entries, print the clarification above the item, then initial and date it.

A Case Report Form will be completed for each participant enrolled into the clinical study. The investigator will review, approve and sign/date each completed CRF. The investigator's signature serves as attestation that all clinical and laboratory data entered on the CRF are complete, accurate and authentic.

The CRF shall contain at a minimum the following components:

- 1) Eligibility documentation, Phone Screen Form
- 2) HIPAA Form
- 3) Demographic Medical History Form
- 4) Individual Data Collection Forms
- 5) Exit and Survey Forms

Record Handling: Data for this study will be entered by the research investigators and study coordinator immediately into the case report form (CRF) for each participant. The data will then be entered into a REDCap database, which uses a MySQL database via a secure web interface with data checks used during data entry to ensure data quality. REDCap includes a complete suite of features to support HIPAA compliance, including a full audit trail, user-based privileges, and integration with the institutional LDAP server. The MySQL database and the web server will both be housed on secure servers operated by the University of Minnesota Academic Health Center's Information Systems group (AHC-IS). The servers are in a physically secure location on campus and are backed up nightly, with the backups stored in accordance with the AHC-IS retention schedule of daily, weekly, and monthly tapes retained for 1 month, 3 months, and 6 months, respectively. Weekly backup tapes are stored offsite. The AHC-IS servers provide a stable, secure, well-maintained, and high-capacity data storage environment, and both REDCap and MySQL are widely-used, powerful, reliable, well-supported systems. Access to the study's data in REDCap will be restricted to the members of the study team by username and password.

Record Keeping: All records and CRFs will be kept in the study coordinator's locked file cabinet in her office until completion of the study. Thereafter the PI will maintain all records for 6 years.

17.2 Data Safety Monitoring.

Adverse Event

An adverse event (AE) is any symptom, sign, illness or experience that develops or worsens in severity during the course of the study. Intercurrent illnesses or injuries will be regarded as adverse events.

Abnormal results of laboratory or diagnostic procedures are considered to be adverse events if the abnormality:

- Results in study withdrawal
- Is associated with a serious adverse event
- Is associated with clinical signs or symptoms
- Leads to additional treatment or to further diagnostic tests
- Is considered by the Investigator to be of clinical significance.

Serious Adverse Event

A serious adverse event (SAE) is any adverse event that is:

- Fatal
- Life-threatening
- Requires or prolongs a hospital stay
- Results in persistent or significant disability or incapacity
- A congenital anomaly or birth defect

Important medical events are events that may not be immediately life-threatening, but are clearly of major clinical significance and may be SAEs. They may jeopardize the participant, and may require intervention to prevent one or the other serious outcomes noted above.

Individual and Entire Study Stopping Rules

- a. Death. Study stopped for both individual and entire trial. Full investigation of event explored by entire study team. The PI and Medical Director will review all details. An event report will be distributed to all governing and monitoring committees.
- b. Transient Functional Decline in Motor and/or Cognitive ability.
 - i. Entire Trial: After the first half of participants are enrolled, the PI will perform an interim safety analysis to determine if the intervention is causing harm. The primary outcome will be performance on the reaching task. We will also consider reports of any adverse events during the study or that occur after participation during a follow-up phone call with the family/participant. If the difference between sham and real tDCS groups exceeds 2 standard deviations in favor of sham tDCS, the study will be stopped at this interim for review by the PI and medical director. If they deem that the protocol has indications for change due to the differences between means, the study will be reviewed by the investigative team and will be changed and submitted for re-approval by the IRB before recommencing the study.
- c. Seizure
 - i. Individual: Removal of child from the study and from any remaining study procedures. Initiation and follow-through of safe and effective

seizure management. Refer to comprehensive seizure management outline (Appendix J) and the complete seizure observation documentation form (Appendix K). Provide Physician letter to participant. (Appendix L).

Study Medical Director Evaluation. Recommend further evaluation to the child and legal guardian for evaluation by pediatric neurologist if not the pediatrician routinely involved in the child's care.

If participant and caregiver are willing, we will assess post-seizure status and potential change of status.

An identification of causality and re-evaluation of treatment design will occur by study researchers, including consultants, medical monitor and physicians in order to proceed. All procedures will be assessed for strict adherence to all intervention steps listed in the protocol. If deviation is found, error will be corrected. Proceed with study.

- ii. Entire Study: If another participant incurs a seizure, proceed with steps for Individual Stopping Rules for Seizure (18.2.c.i). Study will be suspended at this point and thorough review by research team, medical director and consultants will occur in order to assess the need for amendment of the protocol or full stop/termination of study for future safety concerns.
 1. All research procedures will be performed by qualified personnel who have completed required training, including human subjects training. Clinical procedures will be conducted only by personnel who are qualified by training and licensure to perform the procedures.
 2. All personnel will comply with all related regulations and laws, included, but not limited to 45CFR parts 60 and 64, and HIPAA Privacy Regulations. Study data and information will be kept confidential and managed in accordance with requirements of HIPAA. All data (CRF) will be stored in locked offices and not released without participant permission.
 3. Participants will be rigorously screened against inclusion/exclusion criteria to ensure that their participation is safe. This screening begins at the initial discussion in the phone screen, continues with review of the medical record by the PI and Medical Director and Pediatric Neurologist on the study and is again repeated in-person by reviewing the screening documentation.

4. AEs and SAEs will be assessed and followed throughout the study using tools developed by our laboratory (Appendix F). Vital sign monitoring will occur before and after the information.
5. Participants will have contact information to enable them to contact study personnel easily and quickly.

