2.0 Background

2.1 Significance of Research Question/Purpose: Hemiparesis, or weakness on one side of the body, is common following stroke early in life. The broader clinical diagnosis for this type of childhood movement impairment is unilateral cerebral palsy (UCP). Cerebral palsy affects about 3 out of every 1000 live births in the United States¹, and produces lifelong motor, sensory, and cognitive disability.

Neurorehabilitation has primarily focused on intensive motor training to encourage use of the affected extremities in an effort to produce use-dependent neuroplasticity in the brain. Such interventions are effective, but require a burdensome amount of time, 60-90 hours per week, for both the child and therapist. Furthermore, some children do not respond at all to such training.

Neuromodulation is a relatively new field that aims to influence the brain's neuronal activity through direct application of magnetic (TMS) or electric (tDCS) energy. It is thought the combination of neuromodulation and motor training may reduce the dosage of training needed, and would promote recovery to a greater extent for more individuals. Indeed, previous work in adult stroke demonstrate a benefit of combining repetitive TMS (rTMS) and tDCS with motor training, compared to training alone.^{2,3} These types of synergistic interventions are just beginning to be used in children with UCP, with some preliminary data showing potential benefit.

One of the many questions surrounding neuromodulatory interventions like tDCS is how to reliably predict changes in neuronal activity. The currently hypothesized effects of tDCS are polarity-specific: anodal tDCS depolarizes membranes resulting in increased neuronal excitability; cathodal tDCS hyperpolarizes tDCS resulting in decreased neuronal excitability. Furthermore, these effects scale with the intensity of stimulation: the larger

the direct current delivered, the greater the change in excitability. This framework has been used to guide almost all studies using tDCS to produce a change in brain function and resulting behavior.

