5.0 Procedures Involved

5.1 Study Design: This is a randomized, sham-controlled, double-blinded study. The intervention consists of a single, 20 minute session of tDCS paired with motor training (see Figure 2). Participants will be randomized to either real or sham tDCS. The participants and the members of the research team involved in assessments and testing will be blinded to intervention group (real or sham tDCS), but the other research staff/PI/Co-Is will be unblinded.

5.2 Study Procedures:

Pre-study

[figure not shown]

Figure 2. Pre-study timeline and study design.

Participant Screening and Enrollment

Participants will be initially screened for inclusion and exclusion criteria during a phone interview (Appendix A). Initial consent will be obtained over the phone to allow the caregiver to disclose protected health information (PHI) about his/her child. If the family is interested following this phone screen, we will obtain HIPAA consent to perform a medical record review (Appendix B and C). A review is then completed by the study medical director for review of inclusion/exclusion by history and MRI/CT radiographic reports of the brain (Appendix D). Eligibility will be verified by the principal investigator after this review. Eligibility is then discussed with the legal guardian and a formal schedule is established. A pre-study letter will then be sent (Appendix E). Informed consent/assent will be completed before on the day of the MRI acquisition.

The research team will utilize the CMRR Center's screening tools and adhere to the screening SOP during enrollment of all research participants in this protocol. The CMRR Center's screening tools and SOP are IRB approved under the CMRR Center Grant (HSC# 1406M51205) and information regarding screening procedures is publically available on the CMRR website.

Randomization

Participants will be randomly assigned to receive real or sham tDCS. Children with presence of a lesioned hemisphere MEP response may receive 1) ipsilesional anodal; 2) contralesional cathodal tDCS or 3) sham tDCS. Children without a lesioned hemisphere MEP may receive 1) contralesional anodal or 2) sham tDCS. Participants and their families will be blinded to group assignment. Participants will be unblinded after completing the study.

Magnetic Resonance Imaging (MRI) Acquisition

Location: Center for Magnetic Resonance Research (CMRR)

Time: 1 hour (including preparatory time)

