15.0 Data Management

- 15.1 **Data Analysis Plan:** Baseline and demographic information will be summarized by descriptive statistics for continuous variables, and the number and percentage of participants in each category for categorical variables. The primary analysis will compare changes in behavioral and neurophysiologic measures between the two intervention groups (real and sham tDCS). When possible, we will use repeated measures ANOVA to account for differences between groups. If measures are non-normally distributed, we will use Wilcoxon signed-ranks tests. We will use correlation analysis to compare modeled peak electric field strength with changes in behavioral and neurophysiologic outcomes.

Summary of power analysis with alpha of 0.0125 and N per group of 8			
Correlation	MEP		
	Δ	SD	Power
0.3	0.75	0.5	0.71
0.4	0.75	0.5	0.75
0.5	0.75	0.5	0.81
0.6	0.75	0.5	0.87
0.7	0.75	0.5	0.94

- 15.2 **Power Analysis:** With the data and literature available, we completed power calculations for the primary neurophysiological outcome, MEP, and the behavioral clinical outcome, the Assisting Hand Assessment (AHA) scaled score (Table 2). These were based on the difference between the pre- and post-test measurements

adjusting for baseline values, similar to ANCOVA analyses, for added precision. These calculations used the sample size formula for normally distributed statistics with a Bonferroni corrected type I error level of 0.0125 for the four potential primary comparisons between the: 1) Anodal Ipsilesional tDCS group versus Sham_c tDCS, 2) Cathodal Contralesional tDCS versus Sham_c tDCS, 3) Anodal Ipsilesional tDCS group versus Cathodal Contralesional tDCS, and 4) Anodal Contralesional tDCS versus Sham_i tDCS to maintain an overall type I error level of 0.05. Power was computed for 8 participants per treatment group across a range of possible values for the correlation between pre- and post-treatment measurements. These were computed for a change in the MEP of 0.75 mV. The mean change and standard deviation of the MEP in the study population was based on the tDCS/CIMT study. The correlation between pre- and post-treatment MEP in the tDCS/CIMT study was approximately 0.5. Based on these estimates, we will have 81% power to detect a change in the MEP of 0.75 mV, which translates into a large effect size (Cohen's $d = 1.5$).

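### The interim check for functional decline pools three different active montages, so a decline confined to one of them is cut to about a third before it meets the 2 SD limit

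*Combined protocol and SAP*

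**What the plan says.** Section 17.2, stopping rule b.i (transient functional decline), schedules one look: "After the first half of participants are enrolled, the PI will perform an interim safety analysis". The measure is named: "The primary outcome will be performance on the reaching task". The trigger is a single comparison: "If the difference between sham and real tDCS groups exceeds 2 standard deviations in favor of sham tDCS". If it is met, the study stops for review by the PI and medical director. Adverse events are looked at alongside it ("We will also consider reports of any adverse events during the study"), with no numerical trigger and no breakdown by arm. Which SD, which score and which time point are meant is not stated.

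Section 5.1 describes randomisation to real or sham. Section 15.1 likewise speaks of a comparison "between the two intervention groups (real and sham tDCS").

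The randomisation paragraph of section 5.2 sets out five arms in two strata:
- Three arms where the lesioned side responds to TMS: "Children with presence of a lesioned hemisphere MEP response may receive 1) ipsilesional anodal; 2) contralesional cathodal tDCS or 3) sham tDCS".
- Two arms where the lesioned side gives no response: "Children without a lesioned hemisphere MEP may receive 1) contralesional anodal or 2) sham tDCS".

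Section 15.2 names four comparisons at arm level. Three of them set an active montage against sham, with separate sham groups labelled Sham_c and Sham_i. It sizes the trial at 8 per group. Section 10.1 caps enrolment at 40 children with UCP and 10 typically developing children (CTD).

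**The concern.** The three active interventions differ in polarity, in hemisphere, or in both. The background expects polarity to matter: "anodal tDCS depolarizes membranes resulting in increased neuronal excitability", with the reverse for cathodal current. A mean over all real tDCS therefore averages interventions that the plan itself does not expect to act alike. If one montage slows reaching and the other two do not, the pooled mean shows only part of the decline, and the harm check may pass. The remaining children assigned to that montage would then be treated without the review that the rule is meant to prompt. Section 15.2 judges efficacy montage by montage; the check for functional decline does not.

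**Working it through.** The plan states no operating characteristics for the interim rule, so there is no figure to reproduce. The 81% power in section 15.2 is for MEP at the end of the trial; only its group size is used here.

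**Inputs.** 8 per group (15.2) × 5 arms (5.2) = 40, which matches the UCP maximum (10.1). Half of that is 20: 12 real (4 per montage) and 8 sham (4 per stratum). Assumptions: equal arms, normal scores, within-arm SD 1, and a decline of D SD in one montage only.

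**Dilution.** Expected pooled difference = D × 4/12 = D/3. For this to equal 2 SD, D must be 6.

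**Pooled contrast, within-arm SD (five arms, 15 df).** SE = √(1/12 + 1/8) = 0.456. The rule triggers when a noncentral t (15 df, noncentrality (D/3)/0.456) exceeds 2/0.456 = 4.38.

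**Each montage against its own sham, same SD.** SE = √(1/4 + 1/4) = 0.707. The rule triggers when a noncentral t (15 df, noncentrality D/0.707) exceeds 2/0.707 = 2.83.

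| Trigger probability | D = 2 | D = 3 | D = 4 |
|---|---|---|---|
| Pooled, within-arm SD | 1.2% | 4.7% | 14% |
| By montage, within-arm SD | 52% | 90% | 99% |
| Pooled, known SD | 0.17% | 1.4% | 7.2% |
| Pooled, sham-group SD | 3% | 9% | 20% |
| Pooled, SD within the real and sham groups | 0.10% | 0.05% | 0.01% |

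The first two rows are the like-for-like comparison. The known-SD row is 1 − Φ((2 − D/3)/0.456); for D = 3 that is 1 − Φ(2.19) = 1.4%.

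The last row falls as harm grows because the affected arm widens the spread of the mixed real group. The expected real-group variance is 1 + 8D²/33. At D = 3 this is 3.18, the SD over both groups is √((11 × 3.18 + 7)/18) = 1.53, and the expected difference is 1/1.53 = 0.65 of that SD.

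**If 2 standard errors were meant.** With known SD, 1 − Φ(2 − (D/3)/0.456) gives 29% at D = 2 and 58% at D = 3. With the SD estimated within the real and sham groups, simulation gives 17% and 22%.

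**Unequal arms and CTD (known SD).** With 3 to 5 of the 12 real children in the affected montage, the trigger probability at D = 3 runs from 0.3% to 5%. If CTD are included (assumed 15 real, 4 of them affected, against 10 sham), the share is 4/15 = 0.27 and the probabilities at D = 2, 3 and 4 are 0.02%, 0.16% and 1.1%.

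**No harm.** The pooled rule triggers in 0.03% of trials (within-arm SD) to 0.16% (sham SD). The chance that any of the three montage contrasts triggers is 1.8% with the five-arm SD, about 4% with each pair's own SD, and about 9% with the SD of the stratum's sham arm.

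**Strata.** At 8 per arm, 8/16 of sham children but 8/24 of real children lack a lesioned-hemisphere MEP. A stratum gap of G on the interim score would shift the pooled contrast by G × (1/2 − 1/3) = 0.167G. The documents give no value for G.

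**The case against.** **The SD is undefined, so the size is uncertain.** This stands. A reader might infer that the rule almost never triggers. That holds if the SD is taken within the mixed groups, but not for a 4 SD decline with the sham SD (20%), and not if standard errors were meant. The dilution itself occurs under every definition.

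**The wording might already allow arm-level comparison.** The plural in the trigger sentence fits one sham and one real group at least as well, and no interim comparison by montage is described anywhere.

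**Other safeguards exist.** This stands. Deaths and seizures have their own rules whatever the arm, and adverse events are monitored throughout. A reader might infer that this is the only harm rule, or that serious harm would go unseen. The documents do not support either: the item covers transient functional decline. They do not, however, provide another check on that decline by montage.

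**One-montage harm is not shown to be the likely pattern.** This also stands. The opposite polarity effects in section 2.1 concern excitability, not reaching. The same section calls the polarity framework possibly too simple, and it presents inhibition of the non-lesioned side as a way to help the lesioned one. The point needs only that one-montage decline is possible.

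**The stratum imbalance may be harmless.** A reader might infer that it masks harm. The documents do not say that the strata differ on reaching, and change or baseline-adjusted scores would remove much of a baseline difference.

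**Pooling is not the only cause.** This is correct. With known SD, a uniform 1 SD decline in all three montages would trigger the pooled rule in only 1.4% of trials.

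**The stakes are limited.** Each child has one 20-minute session, and a trigger leads to a review.

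**Conclusion.** The concern holds for decline on the reaching task. Read as one real-against-sham contrast, the interim check reduces a one-montage decline to about a third. On a like-for-like SD, its chance of prompting review is about 1%, 5% and 14% for declines of 2, 3 and 4 SD, against 52%, 90% and 99% by montage. Over the SD definitions tried, the pooled figures range over 0.1–3%, 0.05–9% and 0.01–20%. If standard errors were meant, they are 17–29% at 2 SD and 22–58% at 3 SD.

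The figures assume 4 children per arm and normal scores. The documents give neither the allocation ratio nor the stratum mix at the interim. The mixing of strata could add bias in either direction, of unknown size.

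**What to change.** In section 17.2 b.i, leave the limit and its consequence as they are and specify what is compared:
- Compute the difference for each active montage against sham in the same MEP stratum, using the three active-against-sham pairs already listed in section 15.2.
- Name the SD as the within-arm SD pooled over all arms, and state the score and time point.
- Compare CTD real against sham separately.
- Report all real against all sham as supportive, and list adverse events by arm.

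The cost is a few sentences. Section 5.1 leaves the PI, who runs the interim, unblinded, so arm codes can be used without unblinding the assessors. The chance of an unneeded review rises from below 0.2% to about 2% over the three UCP contrasts, and a CTD contrast adds a little. Leaving the SD unnamed could raise it to about 4% or 9%.

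This change does not make the check sensitive to smaller declines: by montage, a 1.5 SD decline in one arm would pass the limit in about 28% of trials.

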15.3 Statistical Analysis: Descriptive analyses of baseline characteristics and outcomes will include means and standard deviations for continuous variables and frequencies for categorical variables. Compliance and tolerance of the intervention will also be evaluated. Safety analyses will be primarily descriptive reporting the number and percentage of any adverse events and will be evaluated and monitored throughout the trial.

This analysis will be conducted based on the intent-to-treat principle to compare the mean neurophysiologic change measured using the MEP from pre- to post- intervention between each tDCS stimulation dose group and sham tDCS adjusted for baseline neurophysiologic measures. Confidence intervals and p-values will be based on robust variance estimation. Statistical significance will be considered as $p < 0.0125$. Supportive analyses may be conducted with consideration of adjustment for residual imbalances between treatment groups after randomization (e.g., gender). The primary analysis will evaluate the change between pre- and post- measurements. A secondary analysis will evaluate the change between pre- and 30 minutes post.

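### The only numerical trigger in the interim harm check, a 2 SD difference on the reaching task, is undefined in its terms and, read plainly, would usually miss a large true worsening

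*Combined protocol and SAP*

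**What the plan says.** Section 17.2 (Individual and Entire Study Stopping Rules, item b.i) states that once half of the participants are enrolled, "the PI will perform an interim safety analysis to determine if the intervention is causing harm". The outcome for this look is named: "The primary outcome will be performance on the reaching task". The numerical rule reads: "If the difference between sham and real tDCS groups exceeds 2 standard deviations in favor of sham tDCS, the study will be stopped at this" look, and the PI and the medical director then review it. The text then speaks of "indications for change due to the differences between means", so the quantity compared is a difference in group means. Safety reports also enter, without a threshold: "We will also consider reports of any adverse events during the study".

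The section does not say which SD is meant, whether post-intervention scores or changes are compared, or which of the assessments at 0, 15, 30 and 60 minutes (section 5.2) is used. It gives no reason for choosing 2 SD and no operating characteristics.

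Two statements elsewhere give a scale. Section 15.2 describes a 0.75 mV change in MEP as one "which translates into a large effect size (Cohen's $d = 1.5"). Section 15.3 says, in the paragraph on MEP change: "Statistical significance will be considered as $p < 0.0125".

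**The concern.** The purpose of the look is to find out whether the intervention is causing harm. A trigger on an observed difference of 2 SD is a high bar with about 20 children. It is also higher, in standardized units, than the one effect that the plan calls large. If the SD is the ordinary spread between children, a substantial slowing on the reaching task could be present in every child given real tDCS and the rule would usually not fire. The second half of enrolment would then go ahead without a mandatory stop. Because the terms are undefined, two people applying the rule to the same data could also reach opposite answers.

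**Working it through.** **Inputs**
- Margin: observed difference above 2 SD favoring sham (17.2 b.i).
- Maximum enrolment: 40 children with UCP and 10 CTD (10.1). Half is 20 (UCP only) or 25 (all).
- 8 per treatment group (15.2), with three real and two sham groups (5.2 Randomization; 15.2). That makes 24 real and 16 sham, so 12 v 8 at half of 40. This split is an assumption, because the documents do not state one for the interim look. For 25 children, 15 v 10 keeps the 3:2 ratio; 14 v 11 and 13 v 12 are nearer to equal. No allocation ratio is given for CTD.
- Normal scores, equal SD, and the same harm in all real montages (assumptions).

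**The plan's own figures.** d = 0.75/0.5 = 1.5, as stated. With baseline adjustment and correlation 0.5, the residual SD is 0.5 x sqrt(1 - 0.25) = 0.433. The standard error at 8 per group is 0.433 x sqrt(2/8) = 0.217. A one-sided t test at 0.0125 on 13 df then gives power 0.811, against the stated 81%; a two-sided one gives 0.707. The benchmark reproduces, and the sidedness of 0.0125 is open.

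**How extreme 2 SD is at 12 v 8.** Standard error of the difference in SD units = sqrt(1/12 + 1/8) = 0.456. t = 2/0.456 = 4.38 on 18 df, two-sided p = 0.0004. For comparison, two-sided 0.0125 is reached at 2.77 x 0.456 = 1.27 SD.

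**Chance that the rule does not fire.** With the SD known, this is Phi((2 - harm)/SE). For a harm of 1.5 SD it is Phi(0.5/0.456) = Phi(1.10) = 0.86. With the SD estimated from the data, the noncentral t (pooled SD) or simulation (sham SD) is used.

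| True worsening, 12 v 8 | SD known | Pooled SD | Sham SD |
|---|---|---|---|
| 1.0 SD | 99% | 96% | 91% |
| 1.5 SD | 86% | 80% | 73% |
| 2.0 SD | 50% | 48% | 45% |

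With 25 children (15 v 10, 14 v 11 or 13 v 12), a 1.5 SD worsening is missed 76-89% of the time.

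**Sensitivity to the undefined SD** (harm of 1.5 raw between-child SDs, 12 v 8, SD known). If the rule uses the SD of change, that harm equals 1.5/sqrt(2(1 - rho)) change SDs:
- rho = 0.5: 1.50 change SDs, missed 86%
- rho = 0.7: 1.94 change SDs, missed 56%
- rho = 0.8: 2.37 change SDs, missed 21%

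The documents give rho only for MEP (about 0.5), and none for the reaching task.

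If standard errors of the difference were meant, the miss rate is Phi(2 - 1.5/0.456) = Phi(-1.29), about 10% at 12 v 8 (11% with an estimated SD) and about 5% at 15 v 10.

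**An added trigger at two-sided 0.0125** (t test, no baseline adjustment). It detects a 1.5 SD worsening 69% of the time at 12 v 8 and 84% at 13 v 12. With no harm it fires wrongly in 0.0125/2 = 0.6% of trials, or 1.25% if the level is one-sided. The 2 SD rule alone fires wrongly in under 0.2% at 12 v 8.

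**The case against.** Several points on the other side stand.

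- The 1.5 SD figure describes MEP. It is neither a reaching-task effect nor a tolerance for harm, so a reader might infer that a 2 SD margin contradicts the plan. It does not; the figure serves only as a yardstick.
- A reader might take the 73-89% range as holding whichever SD is used. The sensitivity figures above show that it does not.
- A reader might say that an observed worsening between 1.27 and 2 SD is significant harm by the trial's own standard. The documents do not support that. The 0.0125 is a Bonferroni level for four named arm-level comparisons. Pooled real versus sham on the reaching task is not one of them, and sidedness is not stated.
- A reader might conclude that anything under 2 SD is passed as no signal and that enrolment continues unreviewed. The text does not say so. The PI performs the analysis, adverse events are considered and are followed throughout the study (17.2), and nothing forbids a review at a smaller difference. The 2 SD rule fixes only when a stop is mandatory.
- Crossing the margin stops the study for review, so a false alarm has a real cost and some height in the margin is defensible.

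What remains is that the only numerical trigger is undefined in three respects and is insensitive on its plain reading. Adverse event reports do not fully replace it, because slower reaching need not be reported as a symptom.

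**Conclusion.** The point holds in a conditional form. On the plain reading (between-child SD, real arms pooled against sham, 12 v 8 assumed), the rule misses a true 1.5 SD worsening 73-86% of the time and a true 2 SD worsening about half the time. The first range becomes 76-89% if about 25 children including CTD are counted. With a known SD, any true harm below the margin is missed more than half the time at any sample size, so on that reading the direction does not depend on the split. It does depend on the SD: the miss rate for 1.5 raw SD falls to 56% or 21% with the SD of change at correlation 0.7 or 0.8, and to about 5-11% with standard errors. The plan should therefore settle the definition and add a more sensitive prompt for review. The documents do not show that the check is unable to detect harm, or that smaller differences would be ignored.

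**What to change.** In section 17.2 b.i:

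1. State that the measure is the baseline-adjusted change in reaching-task time at one named post-intervention time point, and state which SD the 2 SD rule uses.
2. Keep the 2 SD stop. Add a trigger for review by the PI and medical director when the baseline-adjusted pooled real-minus-sham difference favors sham at two-sided p < 0.0125, and report the estimate and its interval to them. Say that this level is borrowed from 15.3 for convenience and was not already set for this comparison.
3. State whether enrolment pauses during the added review. What follows a review stays as the protocol now says.

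The cost is a few sentences and one extra analysis of data already collected, with no more participants or procedures. The downside is about a 0.6% chance of an unneeded review if there is no harm (1.25% if the level is read as one-sided). That figure is for one test at one time point, which is why the time point must be named.
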